4.0 TREATMENT PLAN

4.1 Study Design

This is a phase II open label single-arm study to evaluate the efficacy and safety of nivolumab in patients with AML in complete remission but at high risk for relapse. All patients will be registered in CORe.

4.2 Treatment Plan: Patients will receive nivolumab according to the following treatment plan. Individual minor variations in the initiation of therapy, are acceptable as indicated by patient condition and physician judgment. These variations should be documented in the patient's medical record.

- 4.2.1 Therapy: Patient will receive Nivolumab 3 mg/kg IV every 2 weeks for 6 cycles. One cycle will be defined as 4 weeks (i.e., 2 planned doses of nivolumab).
- 4.2.2 Continuation beyond 6 cycles will be allowed for patients deriving benefit without unacceptable toxicity. The dose after 6 cycles may be modified to an every 4 weeks schedule until 12 months from start of therapy, then every 3 months until disease progression.
- 4.2.3 Patients who discontinue treatment while still in remission or decrease the frequency of administration as described above may have re-treatment at up to every 2 weeks schedule if there is evidence of recurrence of MRD. However, patients with confirmed clinically significant hematologic relapse must be removed from the study.
- 4.2.4 Treatment may continue until the end of therapy as described in section 4.2.2 or until one of the following criteria applies:
 1. Clinically significant progressive disease, or
 2. Intercurrent illness that prevents further administration of treatment, or
 3. Patient request or
 4. General or specific changes in the patient's condition render the patient unacceptable for further treatment in the judgment of the investigator, or
 5. Unacceptable toxicity that in the opinion of the investigator makes it unsafe to continue therapy.

5.0 STUDY MEDICATIONS

5.1 Nivolumab (Anti-PD1)

Nivolumab is a fully human, IgG4 (kappa) isotype, monoclonal antibody that binds PD-1.

Nivolumab will be supplied in vials of 100 mg (10 mg/mL) and packaged in an open-label fashion. Ten nivolumab vials (each 10 mL) will be packaged within a carton. The vials are not subject specific although there will be specific vial assignments by subject distributed by the Pharmacy in order to track drug usage and re-supply.

PRODUCT INFORMATION TABLE: Please also see Drug Information Appendix A

Product Description:(Other names = MDX-1106, ONO-4538, anti-PD-1

Product Description and Dosage	Potency	Primary Packaging (Volume)/Label Type	Secondary Packaging (Qty) /Label Type	Appearance	Storage Conditions (per label)
Nivolumab (BMS-936558-01)* Injection drug product is a sterile, non-pyrogenic, single-use, isotonic aqueous solution formulated at 10 mg/mL	100 mg/Vial (10 mg/mL).	Carton of 5 or 10 vials	10-cc Type 1 flint glass vials stoppered with butyl stoppers and sealed with aluminum seals.	Clear to opalescent, colorless to pale yellow liquid. May contain particles	BMS-936558-01 Injection must be stored at 2 to 8 degrees C (36 to 46 degrees F) and protected from light and freezing

*Nivolumab may be labeled as BMS-936558-01 Solution for Injection

5.1.1 Dose Calculation of nivolumab

Total dose should be calculated as in the following example:

Subject's actual body weight in kg x 3 mg = total dose in mg

Therefore, a subject weighing 70 kg who is to receive a dose of 3 mg/kg would be administered 210 mg of nivolumab (70 kg x 3 mg/kg = 210 mg).

5.1.2 Preparation and Dispensing of Nivolumab

The product storage manager should ensure that the study drug is stored in accordance with the environmental conditions (temperature, light, and humidity) as determined by the Investigator Brochure. If concerns regarding the quality or appearance of the study drug arise, do not dispense the study drug and contact Bristol Myers Squibb immediately.

Investigational product documentation must be maintained that includes all processes required to ensure drug is accurately administered. This includes documentation of drug storage, administration and, as applicable, storage temperatures, reconstitution, and use of required processes (e.g. required diluents, administration sets).

Nivolumab vials must be stored at a temperature of 2°C to 8°C and should be protected from light. If stored in a glass front refrigerator, vials should be stored in the carton.

Recommended safety measures for preparation and handling of nivolumab include laboratory coats and gloves.

For details on prepared drug storage and use time of nivolumab under room temperature/light and refrigeration, please refer to the Investigator Brochure section for “Recommended Storage and Use Conditions”. Care must be taken to assure sterility of the prepared solution as the product does not contain any anti-microbial preservative or bacteriostatic agent. No incompatibilities between nivolumab and polyolefin bags have been observed.

Nivolumab is to be administered as an approximately 60 minute IV infusion, using a volumetric pump with a 0.2/0.22 micron in-line filter at the protocol-specified dose. The drug can be diluted with 0.9% normal saline for delivery but the total drug concentration of the solution cannot be below 1 mg/dl. It is not to be administered as an IV push or bolus injection. At the end of the infusion, flush the line with a sufficient quantity of normal saline.

5.1.3 Administration of nivolumab

Patients will receive nivolumab as a 60 minute IV infusion on Day 1 and 15 (+/- 3days) of a 28 day treatment cycle. Patients may be dosed no less than 12 days from the previous dosing of nivolumab. Dosing calculations should be based on the actual body weight. If the patient’s weight on the day of dosing differs by > 10% from the weight used to calculate the original dose, the dose must be recalculated. All doses should be rounded to the nearest milligram. There will be no dose modifications allowed.

5.1.4 Patient Monitoring During Infusion

Patient vital signs should be monitored prior to dosing, about 15 minutes after initiation of the infusion (then every 15-20 minutes as indicated), at 60 and 120 minutes after completion of the infusion, or longer if indicated, until the vital signs normalize or return to baseline. For subsequent infusions, vital signs should be collected prior to dosing, every 30 minutes during dosing, and 1 hour post dosing.

5.1.5 Treatment of nivolumab Related Infusion Reactions

Since nivolumab contains only human immunoglobulin protein sequences, it is unlikely to be immunogenic and induce infusion or hypersensitivity reactions. However, if such a reaction were to occur, it might manifest with fever, chills, rigors, headache, rash, pruritis, arthralgias, hypo- or hypertension, bronchospasm, or other symptoms. All Grade 3 or 4 infusion reactions should be reported within 24 hours to BMS. Grade 3 or 4 infusion reactions will also be reported as an SAE if criteria are met as defined in section 8.4. Infusion reactions should be graded according to NCI CTCAE (version 4.0) guidelines.

Treatment recommendations for nivolumab related infusion reactions are provided below and may be modified based on MD Anderson treatment standards and guidelines, as appropriate:

For Grade 1 symptoms (Mild reaction; infusion interruption not indicated; intervention not indicated): Remain at bedside and monitor subject until recovery from symptoms. The following prophylactic premedications are recommended for future infusions: diphenhydramine 50 mg (or equivalent) and/or acetaminophen 325 to 1000 mg at least 30 minutes before additional nivolumab administrations.

For Grade 2 symptoms (Moderate reaction requires therapy or infusion interruption but responds promptly to symptomatic treatment [e.g. antihistamines, non-steroidal anti-inflammatory drugs, narcotics, corticosteroids, bronchodilators, IV fluids]; prophylactic medications indicated for ≤ 24 hours):

Stop the nivolumab infusion, begin an IV infusion of normal saline, and treat the subject with diphenhydramine 50 mg IV (or equivalent) and/or acetaminophen 325 to 1000 mg; remain at bedside and monitor subject until resolution of symptoms. Corticosteroid or bronchodilator therapy may also be administered as appropriate. If the infusion is interrupted, then restart the infusion at 50% of the original infusion rate when symptoms resolve; if no further complications ensue after 30 minutes, the rate may be increased to 100% of the original infusion rate. Monitor subject closely. If symptoms recur then no further nivolumab will be administered at that visit. Administer diphenhydramine 50 mg IV, and remain at bedside and monitor the subject until resolution of symptoms. The amount of study drug infused must be recorded on the case report form (CRF). The following prophylactic premedications are recommended for future infusions: diphenhydramine 50 mg (or equivalent) and/or acetaminophen 325 to 1000 mg should be administered at least 30 minutes before additional nivolumab administrations. If necessary, corticosteroids (recommended dose: up to 25 mg of IV hydrocortisone or equivalent) may be used.

For Grade 3 or Grade 4 symptoms [Severe reaction, Grade 3: prolonged (i.e. not rapidly responsive to symptomatic medication and/or brief interruption of infusion); recurrence of symptoms following initial improvement; hospitalization indicated for other clinical sequelae (e.g. renal impairment, pulmonary infiltrates), Grade 4: life-threatening; pressor or ventilatory support indicated]:

Immediately discontinue infusion of nivolumab. Begin an IV infusion of normal saline, and treat the subject as follows: Recommend bronchodilators, epinephrine 0.2 to 1 mg of a 1:1,000 solution for subcutaneous administration or 0.1 to 0.25 mg of a 1:10,000 solution injected slowly for IV administration, and/or diphenhydramine 50 mg IV with methylprednisolone 100 mg IV (or equivalent), as needed. Subject should be monitored until the investigator is comfortable that the symptoms will not recur. Nivolumab will be permanently discontinued. Institutional guidelines will be followed for the treatment of anaphylaxis. Remain at bedside and monitor subject until recovery from symptoms. In the case of late-occurring hypersensitivity symptoms (e.g. appearance of a localized or generalized pruritus within 1 week after treatment), symptomatic treatment may be given (e.g. oral antihistamine or corticosteroids).

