5.1.6 Dose Modification

Dose reductions or dose escalations are not permitted.

5.2 Dose Delay Criteria:

Because of the potential for clinically meaningful nivolumab-related AEs requiring early recognition and prompt intervention, management algorithms have been developed for suspected AEs of selected categories.

Dose delay criteria apply for all drug-related adverse events

Nivolumab administration should be delayed for the following:

- Any Grade \geq 2 non-skin, drug-related AE, with the following exceptions:
 - Grade 2 drug-related fatigue or laboratory abnormalities do not require a treatment delay, However, dose delays should occur for the following laboratory abnormalities:
 - G2 Creatinine, or
 - G2 ALT, AST or total bilirubin
- Any Grade 3 skin, drug-related AE
- Any Grade 3 drug-related laboratory abnormality, with the following exceptions for lymphopenia, leukopenia, AST, ALT, total bilirubin, or asymptomatic amylase or lipase:
 - Grade 3 lymphopenia or leukopenia does not require dose delay.
 - Grade 3 AST, ALT or total bilirubin requires permanent discontinuation of nivolumab
- Any AE, laboratory abnormality, or intercurrent illness which, in the judgment of the investigator, warrants delaying the dose of study medication.

5.3 Criteria to Resume Treatment:

Subjects may resume treatment with study drug when the drug-related AE(s) resolve to Grade ≤ 1 or baseline value, with the following exceptions:

- Subjects may resume treatment in the presence of Grade 2 fatigue
- Subjects who have not experienced a Grade 3 drug-related skin AE may resume treatment in the presence of Grade 2 skin toxicity
- Drug-related pulmonary toxicity, diarrhea, or colitis, must have resolved to baseline before treatment is resumed
- Drug-related endocrinopathies adequately controlled with only physiologic hormone replacement may resume treatment

If the criteria to resume treatment are met, the subject should restart treatment at the next scheduled timepoint per protocol. However, if the treatment is delayed past the next scheduled timepoint per protocol, the next scheduled timepoint will be delayed until dosing resumes.

If treatment is delayed > 6 weeks, the subject must be permanently discontinued from study therapy, except as specified in discontinuation section.

5.4 Management Algorithms:

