Immuno-oncology (I-O) agents are associated with AEs that can differ in severity and duration than AEs caused by other therapeutic classes. Nivolumab is considered an immuno-oncology agent in this protocol. Early recognition and management of AEs associated with immuno-oncology agents may mitigate severe toxicity. Management algorithms have been developed to assist investigators in assessing and managing the following groups of AEs: Gastrointestinal, Renal, Pulmonary, Hepatic, Endocrinopathies, Skin, Neurological.

For subjects expected to require more than 4 weeks of corticosteroids or other immunosuppressants to manage an AE, consider recommendations provided in the algorithms. These algorithms are found in Appendix B of this protocol. The guidance provided in these algorithms should not replace the Investigator's medical judgment but should complement it.

5.5 Discontinuation Criteria:

Treatment should be permanently discontinued for the following:

- Any Grade 2 drug-related uveitis or eye pain or blurred vision that does not respond to topical therapy and does not improve to Grade 1 severity within the re-treatment period OR requires systemic treatment
- Any Grade 3 non-skin, drug-related adverse event lasting > 7 days, with the following exceptions for drug-related laboratory abnormalities, uveitis, pneumonitis, bronchospasm, diarrhea, colitis, neurologic adverse event, hypersensitivity reactions, and infusion reactions:
 - Grade 3 drug-related uveitis, pneumonitis, bronchospasm, diarrhea, colitis, neurologic adverse event, hypersensitivity reaction, or infusion reaction **of any duration** requires discontinuation
 - Grade 3 drug-related laboratory abnormalities do not require treatment discontinuation except those noted below:
 - Grade 3 drug-related thrombocytopenia > 7 days or associated with bleeding requires discontinuation
 - Grade 3 drug-related ALT, AST or total bilirubin require discontinuation:
- Any Grade 4 drug-related adverse event or laboratory abnormality, except for the following events which do not require discontinuation:
 - Isolated Grade 4 amylase or lipase abnormalities that are not associated with symptoms or clinical manifestations of pancreatitis and decrease to < Grade 4 within 1 week of onset.

- Isolated Grade 4 electrolyte imbalances/abnormalities that are not associated with clinical sequelae and are corrected with supplementation/appropriate management within 72 hours of their onset

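### A nivolumab infusion reaction that recurs after restart is handled as Grade 2 and stopped for that visit, although the protocol's own Grade 3 definition covers it and requires permanent discontinuation

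*Combined protocol and SAP*

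**What the plan says.** Section 5.1.5 sets the grading standard, "Infusion reactions should be graded according to NCI CTCAE (version 4.0) guidelines", and then gives instructions by grade.

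- **Grade 2 branch.** The infusion is stopped and symptoms are treated. If it was interrupted, staff are to "restart the infusion at 50% of the original infusion rate when symptoms resolve". On recurrence: "If symptoms recur then no further nivolumab will be administered at that visit". Later in the paragraph: "The following prophylactic premedications are recommended for future infusions". Patients whose symptoms recurred are not excluded from that advice.
- **Grade 3 or 4 branch.** The Grade 3 definition has three items separated by semicolons, one of which is "recurrence of symptoms following initial improvement". The action is "Nivolumab will be permanently discontinued".
- **Section 5.5.** The list "Grade 3 drug-related uveitis, pneumonitis, bronchospasm, diarrhea, colitis, neurologic adverse event, hypersensitivity reaction, or infusion reaction" leads to discontinuation whatever the duration.
- **Sections 5.2 and 5.3.** A drug-related Grade 2 non-skin event delays dosing. Once it has resolved to Grade 1 or baseline, "the subject should restart treatment at the next scheduled timepoint per protocol".
- **Reporting.** Section 5.1.5 requires Grade 3 and 4 infusion reactions to reach the supporting company within 24 hours.

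**The concern.** The Grade 2 branch contains an event that the protocol itself defines as Grade 3, and gives it a weaker action. No sentence moves that event from one branch to the other. Bedside staff who read the Grade 2 paragraph in order reach an instruction limited to the current visit, followed by advice on how to premedicate next time.

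The assigned grade decides three things: whether the patient may be dosed again, whether the 24-hour report is due, and whether the event can count in the section 9.0 toxicity monitoring (if it is treatment-related and clinically significant). The first is the serious one, because it means giving the drug again to a patient who has met the protocol's criterion for a severe reaction.

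**Working it through.** **Tracing one patient through the text.** The main check is a reading of the rules, not a calculation.

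1. A Grade 2 reaction occurs and the infusion is interrupted.
2. The restart condition in 5.1.5 is that symptoms have resolved. Anything that returns afterwards therefore follows an initial improvement.
3. Symptoms return at half rate.

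| Route | Rule applied | Result |
|---|---|---|
| Stay in the Grade 2 branch | 5.1.5 Grade 2, then 5.2 and 5.3 | Stop for this visit, wait for Grade 1 or baseline, resume at the next scheduled dose, premedication advised; no 24-hour report |
| Regrade as Grade 3 | 5.1.5 Grade 3 or 4, and 5.5 | Permanent discontinuation; 24-hour report |

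The two routes agree on the day of the event and part at the next scheduled dose. Sections 5.2 and 5.3 do not reconcile them: for an event left at Grade 2 they point towards resuming.

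**How often this could arise.** Inputs are from the select adverse event table in section 2.4.2.4.

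- Higher-grade infusion reactions at 3 mg/kg: 0/54. Exact two-sided 95% upper limit = 1 − 0.025^(1/54) = 6.6%. In 30 patients: 30 × 0.066 = 1.98, about 2.
- Higher-grade, all doses: 2/306 = 0.65%. Expected in 30: 30 × 2/306 = 0.196. Chance of at least one: 1 − (1 − 2/306)^30 = 17.9%. Both events were hypersensitivity at 10 mg/kg.
- Any grade: 15/306 = 4.9% and 3/54 = 5.6%. These include Grade 1 reactions that need no interruption, so they are only loose upper bounds.

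Two cautions apply. The higher-grade column is labelled Grade 2-4, but its totals for diarrhea (3) and pruritus (1) equal the Grade 3-4 counts in the section 2.4.2.3 table. The label may therefore be wrong, and the Grade 2 count would then be unknown. Also, the documents do not say what share of interrupted infusions has a recurrence after restart; I assume a range from none to all.

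**Is the toxicity rule affected?** Under section 9.0 the prior is Beta(0.6, 1.4), and the trial stops if Pr(π_T > 0.30 | data) > 0.88, from patient 10. With x toxicities in n patients the posterior is Beta(0.6 + x, 1.4 + n − x). The smallest x that crosses 0.88 is:

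| n | 10–12 | 13–15 | 16–18 | 19–20 | 21–23 | 24–26 | 27–29 |
|---|---|---|---|---|---|---|---|
| x | 6 | 7 | 8 | 9 | 10 | 11 | 12 |

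All match the protocol. Exact early-stopping probabilities, computed patient by patient, are 0.0353 at a true rate of 20% and 0.2447 at 30%, both equal to the protocol's table. At 17% (52/306, the treatment-related Grade 3-4 rate in section 2.4.2.3) the probability is 1.48%; at 16%, an illustrative one-point drop from under-grading, it is 1.06%. The 17% covers all treatment-related Grade 3-4 events, a wider class than the rule counts, so it serves only to show scale.

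**The case against.** The strongest reply is that the instructions do not strictly collide. Withholding drug at that visit is compatible with never giving it again, and the sentence does not say that the patient may be re-dosed. The premedication advice sits under the Grade 2 heading, and a patient who now meets the Grade 3 definition is no longer under it. CTCAE grading is required, the Grade 3 definition is printed in the very next paragraph, and 5.5 repeats the permanent stop. Section 5.1.5 also describes its treatment paragraphs as recommendations that local standards may modify, while 5.5 has no such clause for infusion reactions. On this view the reporting failure happens only if staff misgrade, the number of patients affected could be zero, and the toxicity arithmetic is beside the point.

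Much of this stands. On a careful reading 5.5 controls, the event is rare, its frequency cannot be fixed from the documents, and the toxicity calculation serves only to show that the rule is not at fault.

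It does not remove the problem. The recurrence sentence names the event inside the Grade 2 branch, gives it its own action, limits that action to one visit, and is followed by advice for future infusions without excepting this patient. Permission to adapt treatment does not tell staff which branch applies. An instruction that is safe only if the reader overrides it with a later paragraph should be corrected.

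**Conclusion.** The concern holds. A recurrence after restart meets the protocol's Grade 3 criterion, yet the Grade 2 branch, followed as written, allows re-dosing and can leave the 24-hour report undone. This is a patient-safety and consistency fault, not an error in the statistical design.

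The expected number affected is small. If the background rates carry over to this population, about 0.2 higher-grade infusion reactions are expected in 30 patients from the pooled data, and up to about 2 at the upper limit for 3 mg/kg. These figures depend on a column label that may be wrong, and the share recurring after restart is unknown. The effect on early stopping for toxicity is negligible: 1.48% against 1.06% in the illustration. The change should be made because the possible harm is serious and the correction is simple; the conclusion itself rests on the text and not on the rates.

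**What to change.** Replace the Grade 2 recurrence sentence in 5.1.5 with wording such as: if symptoms recur after restart, stop the infusion, grade the event as Grade 3, and follow the Grade 3 instructions, including permanent discontinuation under 5.5 and the 24-hour report; count it in the section 9.0 toxicity monitoring if it is treatment-related and clinically significant. Limit the Grade 2 premedication advice to reactions that do not recur. If the sponsor does intend rechallenge after a recurrence, that exception should be written into both 5.1.5 and 5.5.

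The cost is one or two sentences through an amendment, with no new data or procedures and no change to the endpoint, sample size, boundaries or analysis. The downside of the stricter wording is that an occasional patient with a manageable recurrence comes off treatment, which the Grade 3 instruction and 5.5 already require.

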5.1.6 Dose Modification

Dose reductions or dose escalations are not permitted.

5.2 Dose Delay Criteria:

Because of the potential for clinically meaningful nivolumab-related AEs requiring early recognition and prompt intervention, management algorithms have been developed for suspected AEs of selected categories.

Dose delay criteria apply for all drug-related adverse events

Nivolumab administration should be delayed for the following:

- Any Grade \geq 2 non-skin, drug-related AE, with the following exceptions:
 - Grade 2 drug-related fatigue or laboratory abnormalities do not require a treatment delay, However, dose delays should occur for the following laboratory abnormalities:
 - G2 Creatinine, or
 - G2 ALT, AST or total bilirubin
- Any Grade 3 skin, drug-related AE
- Any Grade 3 drug-related laboratory abnormality, with the following exceptions for lymphopenia, leukopenia, AST, ALT, total bilirubin, or asymptomatic amylase or lipase:
 - Grade 3 lymphopenia or leukopenia does not require dose delay.
 - Grade 3 AST, ALT or total bilirubin requires permanent discontinuation of nivolumab
- Any AE, laboratory abnormality, or intercurrent illness which, in the judgment of the investigator, warrants delaying the dose of study medication.

5.3 Criteria to Resume Treatment:

Subjects may resume treatment with study drug when the drug-related AE(s) resolve to Grade ≤ 1 or baseline value, with the following exceptions:

- Subjects may resume treatment in the presence of Grade 2 fatigue
- Subjects who have not experienced a Grade 3 drug-related skin AE may resume treatment in the presence of Grade 2 skin toxicity
- Drug-related pulmonary toxicity, diarrhea, or colitis, must have resolved to baseline before treatment is resumed
- Drug-related endocrinopathies adequately controlled with only physiologic hormone replacement may resume treatment

If the criteria to resume treatment are met, the subject should restart treatment at the next scheduled timepoint per protocol. However, if the treatment is delayed past the next scheduled timepoint per protocol, the next scheduled timepoint will be delayed until dosing resumes.

If treatment is delayed > 6 weeks, the subject must be permanently discontinued from study therapy, except as specified in discontinuation section.

5.4 Management Algorithms:

Immuno-oncology (I-O) agents are associated with AEs that can differ in severity and duration than AEs caused by other therapeutic classes. Nivolumab is considered an immuno-oncology agent in this protocol. Early recognition and management of AEs associated with immuno-oncology agents may mitigate severe toxicity. Management algorithms have been developed to assist investigators in assessing and managing the following groups of AEs: Gastrointestinal, Renal, Pulmonary, Hepatic, Endocrinopathies, Skin, Neurological.

For subjects expected to require more than 4 weeks of corticosteroids or other immunosuppressants to manage an AE, consider recommendations provided in the algorithms. These algorithms are found in Appendix B of this protocol. The guidance provided in these algorithms should not replace the Investigator's medical judgment but should complement it.

5.5 Discontinuation Criteria:

Treatment should be permanently discontinued for the following:

- Any Grade 2 drug-related uveitis or eye pain or blurred vision that does not respond to topical therapy and does not improve to Grade 1 severity within the re-treatment period OR requires systemic treatment
- Any Grade 3 non-skin, drug-related adverse event lasting > 7 days, with the following exceptions for drug-related laboratory abnormalities, uveitis, pneumonitis, bronchospasm, diarrhea, colitis, neurologic adverse event, hypersensitivity reactions, and infusion reactions:
 - Grade 3 drug-related uveitis, pneumonitis, bronchospasm, diarrhea, colitis, neurologic adverse event, hypersensitivity reaction, or infusion reaction **of any duration** requires discontinuation
 - Grade 3 drug-related laboratory abnormalities do not require treatment discontinuation except those noted below:
 - Grade 3 drug-related thrombocytopenia > 7 days or associated with bleeding requires discontinuation
 - Grade 3 drug-related ALT, AST or total bilirubin require discontinuation:
- Any Grade 4 drug-related adverse event or laboratory abnormality, except for the following events which do not require discontinuation:
 - Isolated Grade 4 amylase or lipase abnormalities that are not associated with symptoms or clinical manifestations of pancreatitis and decrease to < Grade 4 within 1 week of onset.

- Isolated Grade 4 electrolyte imbalances/abnormalities that are not associated with clinical sequelae and are corrected with supplementation/appropriate management within 72 hours of their onset
- Any dosing interruption lasting > 6 weeks with the following exceptions:
 - Dosing interruptions to allow for prolonged steroid tapers to manage drug-related adverse events are allowed. Prior to re-initiating treatment in a subject with a dosing interruption lasting > 6 weeks, the Investigator must be consulted. Tumor assessments should continue as per protocol even if dosing is interrupted
 - Dosing interruptions > 6 weeks that occur for non-drug-related reasons may be allowed if approved by the Investigator. Prior to re-initiating treatment in a subject with a dosing interruption lasting > 6 weeks, the Investigator must be consulted. Tumor assessments should continue as per protocol even if dosing is interrupted
- Any adverse event, laboratory abnormality, or intercurrent illness which, in the judgment of the Investigator, presents a substantial clinical risk to the subject with continued nivolumab dosing

